5.7 Single agent BI-1206 expansion cohort (Part B, Arm 1)

On determining the RP2D of single agent BI-1206 in Part A, Arm 1, up to 25 further patients will be enrolled into an expanded single agent cohort (Part B, Arm 1) at that dose level for further evaluation of toxicity and efficacy. This cohort will include a minimum of 12 chronic lymphocytic leukaemia (CLL) and six mantle cell lymphoma (MCL) patients.

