Assessing the safety and toxicity profile of: 
• BI-1206 as a single agent in Arm 1 at the RP2D as determined in Part A (Part B, Arm 1)• BI-1206 when given in combination with an anti-CD20 monoclonal at the RP2D combination dose as determined in Part A (Part B, Arm 2)	Documenting AEs, SAEs (graded according to NCI-CTCAE Version 4.02) and laboratory parameters and determining their causality in relation to BI-1206 and, where appropriate, anti-CD20 antibody. Causality of AEs/SAEs will be assessed by the Investigator.

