3.3 Definition of dose limiting toxicity

Some of the dose limiting toxicity (DLT) and maximum tolerated dose (MTD) definitions are derived from the National Cancer Institute (NCI) Common Terminology Criteria for Adverse Events (CTCAE) Version 4.02. Please note that not all of the events described as DLTs are fully supported by NCI CTCAE but are formed by amalgams of different events in order to assist with assessments of adverse events.

The definition of DLT applies to both the single agent and combination dose escalation arms (Part A of the study [boxes outlined in red in Figure 2]).

A DLT is defined as a highly probably or probably **BI-1206 or rituximab-related AE occurring during** the four weeks of induction treatment and up to one week post the fourth infusion of BI-1206 (i.e. by Day 28/Week 5) which fulfils one or more of the following criteria:

- Neutropenia or neutrophil count decrease Grade 4 ($ANC < 0.5 \times 10^9/L$) for >10 days duration
*see note despite growth factor support
- Febrile neutropenia (fever of unknown origin without clinically or microbiologically documented infection) with Grade 3 or 4 neutropenia (absolute neutrophil count [ANC] $<1.0 \times 10^9/L$) and fever $\geq 38.5^\circ C$).
- Infection (documented clinically or microbiologically) with Grade 3 or 4 neutropenia ($ANC < 1.0 \times 10^9/L$)
- Thrombocytopenia or platelet count decrease Grade 4: a) for ≥ 5 days*see note, or b) associated with active bleeding, or c) requiring platelet infusion
- Grade 3 or 4 non-haematological toxicity. This includes Grade 3 and 4 biochemical AEs as DLTs.

EXCLUDING:

- Grade 3 or 4 nausea or vomiting in patients who have not received optimal treatment with anti-emetics
- Grade 3 or 4 diarrhoea in patients who have not received optimal treatment with anti-diarrhoeals
- Alopecia
- Grade 3 infusion related reactions
- Transient, asymptomatic Grade 3 biochemical abnormalities if agreed by the Sponsor and the study team, including the Chief Investigator
- Event with a fatal outcome.

***Note: In the event of a Grade 4 neutropenia or Grade 4 thrombocytopenia, a full blood count must be performed at least on Day 10 (Day 5 for thrombocytopenia) after the onset of the event to determine if a DLT has occurred. The investigator must continue to monitor the patient closely until resolution to Grade 3 or less. Please See [Section 5.9.4](#) 'Management of thrombocytopenia (Grade 4)' for further details.**

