5.3 Communication Plan where dose escalation (Part A) is to occur

5.3.1 Organisation and preparation for dose decision meetings.

Dose decision meetings will be organised by the Sponsor for weekly review of patient data during the first three weeks of the intra-patient dose escalation cohort in Arm 1 only, and subsequently during or following Week 5 of the last patient recruited to each cohort in Arm 1 or in Arm 2. Dose decision meetings will be triggered and occur independently for each treatment arm.

Required attendees/functional groups are as defined in the Sponsor's SOP: Sponsor Pharmacovigilance (PV) representative, Sponsor Medical Sciences representative (MS), Sponsor Clinical Study Manager or appropriate delegate, CI and PIs with patients at their sites undergoing review (a nominated sub- or co-investigator may attend in the PI's place if necessary). Optional attendees are Research Nurses or other relevant site staff and the following Sponsor representatives; Clinical Research Associates (CRAs), Clinical Study Co-ordinator (CSC), Clinical Data Manager (CDM) and, Project Leader (PL). PI's who do not have patients in the cohort under review are encouraged to attend but not required.

Prior to the dose decision meeting, the Sponsor will distribute the agenda and all necessary data to the meeting attendees and all study PIs if they are not available to attend the meeting, specifying which patients and data will form part of the review. The essential data to be reviewed to make decisions concerning changes in dose will be defined in the monitoring guidelines for the study. These will consist primarily of clinical data listings from Data Management (DM), safety data listings from PV and available pharmacokinetic and pharmacodynamic (PK/PD) assay data.

For intra-patient dose escalation, in order to ensure that the most recent trial data is under review data listings will be reviewed alongside anonymised safety data signed off by the site Investigator and faxed or emailed from site directly.

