^a Assumes that no clinically relevant ≥Grade 2 related toxicity has occurred

^b Assumes that no DLTs are encountered and is also dependant on number of patients that need to be replaced (if patient withdraws for reasons other than DLT).

5.4.1 Action if DLT observed in Cohort 1 (0.4mg to 50 mg), Part A Arm 1

Cohort 1 will consist of a minimum of a single patient, with intra patient dose escalation permitted up to a maximum weekly dose of 50 mg. Safety data will be reviewed on a weekly basis prior to the next planned dose and a decision to dose-escalate will be made based on this data.

If a DLT is observed at or below a dose of 50 mg the cohort will be expanded to up to six patients at the dose level at which the DLT is first identified (the most recent dose prior to onset of the event identified as a DLT). If one out of the six patients experiences DLT, intra-patient dose escalation will cease but standard dose escalation will continue; subsequent cohorts will be expanded to three patients. If two or more out of the six patients experiences a DLT, decisions about future patients will be made in accordance with Figure 4.

5.4.2 Dose escalation and action if clinically relevant \geq Grade 2 related toxicity observed at dose levels from Cohort 2 onwards, Part A Arm 1

From Cohort 2 onwards, all cohorts will include a minimum of one patient (see Figure 4)

- In the first patient recruited, any episode of clinically relevant \geq Grade 2 related toxicity would trigger cohort expansion to a minimum of 3 patients.
- Clinical relevance of the related toxicity will be determined by review and agreement between the relevant Investigator, Chief Investigator and Sponsor according to the following definition:

[figure not shown]
The test of clinical relevance is that the adverse event in question would cause the Investigator to re-evaluate the risk-benefit assessment of continuing therapy for the patient experiencing the event and to conclude that on a balance of probabilities, the risk-benefit ratio could be materially worsening

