- The decision to expand a minimum of one patient cohort to a 3+3 cohort following a clinically relevant \geq Grade 2 related toxicity will be documented and distributed by the Sponsor to all Investigators as per Section 5.3.4. The decision may occur outside the dose decision meetings as it is dependent on when the event/s occurs. The assessment of a clinically relevant toxicity will end at Week 5 (same as the DLT period i.e. one week post fourth infusion).
- As per Section 9.4, related toxicity will be highly probably, probably and possibly related to BI-1206 (or rituximab in Arm 2).

It should be noted that dose escalation and cohort size decisions will be made based on data from completed cohorts in the single agent arm (Arm 1); available data from the combination arm (Arm 2) will be also be reviewed and considered in the Arm 1 dose decision meetings. Please refer to Section 5.3 for details of the communication plan, the process for dose escalation review and decision making and the dissemination of information.

All patients in a cohort must have completed induction therapy and 7 days post the fourth infusion for dose-escalation to the next cohort to occur. The second patient in any cohort will not commence treatment until after the first patient in that cohort has completed two infusions of BI-1206; the third patient in any cohort will not commence treatment until after the second patient in that cohort has completed one infusion of BI-1206.

Figure 4: Dose escalation decision-making and action if clinically relevant \geq Grade 2 related toxicity and/ or DLT observed at dose levels from Cohort 2 (Part A, Arm 1)

dx = initial dose level dx +1 = 1 level above initial dose

5.4.3 Dose escalation and action if a DLT observed at dose levels from Cohort 2 onwards, Part A, Arm 1

If one instance of DLT is observed in any cohort, the cohort will be expanded to include up to six patients. If one out of the six patients experience a DLT then dose escalation will continue, and the next cohort will consist of a minimum of 3 patients as described in Figure 4. If no DLTs are seen in 3 patients, further escalations will continue as 3+3 cohorts.

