The BI-1206 doses explored in Part A, Arm 2 may follow the dose levels outlined in Table 1 but will be dependent on emerging data. Intermediate BI-1206 doses may be examined, e.g. a dose between 400 mg and 800 mg could be chosen for further investigation based on a review of the emerging safety data but in any event, dose increases will not exceed those described in Table 1. Intermediate dose levels will only be explored if deemed clinically appropriate after review of a completed cohort in Arm 2 and agreed in dose decision meeting (see [Section 5.3](#)).

The maximum weekly BI-1206 dose to be administered will be 800 mg in both Arm 1 and Arm 2.

5.6 Cohort expansion at maximum tolerated and/or maximum administered dose (Part A, Arm 1 and Arm 2)

Cohorts may be expanded to six patients as described in Sections 5.4.1 and 5.4.2. If only one out of six patients experiences a DLT, dose escalation will continue. If two out of up to six (i.e. between two and six) patients experience a DLT dose escalation will stop and this dose will be defined as the maximum administered dose (MAD). At least six patients will be treated at a dose below the MAD to define the MTD.

The MAD could also equal the MTD in the event that dose escalation is stopped before two DLTs are observed at a given dose level due to the expectation that higher dose levels would be too toxic to administer to patients, or if the 800 mg dose level is reached.

The single agent RP2D in Part B, Arm 1 of the proposed clinical trial will be determined by the Sponsor, CI and PIs, following review of all available PK/PD and clinically relevant toxicity data for all patients entered onto the trial in Part A (Arm 1 and Arm 2), and the identified MTD or MAD.

The combination RP2D in Part B, Arm 2 of the proposed clinical trial will be determined by the Sponsor, CI and PIs, following review of all available PK/PD and clinically relevant toxicity data for all patients entered onto the trial in Part A (Arm 1 and Arm 2), and the identified MTD or MAD.

Any available data from other trials investigating BI-1206 will also be considered in defining the RP2D in Arm 1 and Arm 2. The RP2D for each arm may be the same or different but it will not exceed 800 mg as per Table 1.

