5.8 BI-1206 and rituximab combination expansion cohort (Part B, Arm 2)

On determining the RP2D of BI-1206 in combination with rituximab in Part A, Arm 2, up to 25 further patients will be enrolled into an expanded combination cohort (Part B, Arm 2) at that dose level for further evaluation of toxicity and efficacy. This cohort will include a minimum of 12 CLL and six MCL patients.

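### Part B enrols up to 25 patients per arm with no cohort-level toxicity count and no scheduled cohort-level safety review; the oversight that reaches it is continuous but discretionary

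*Combined protocol and SAP*

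**What the plan says.** Two expansion arms follow the escalation. In Section 5.7, "up to 25 further patients will be enrolled into an expanded single agent cohort (Part B, Arm 1) at that dose level"; in Section 5.8, "up to 25 further patients will be enrolled into an expanded combination cohort (Part B, Arm 2) at that dose level". Neither section gives an event count, a staging of enrolment or a review point. Section 3.1.1 makes the safety and toxicity profile the primary objective of Part B, for example for "BI-1206 as a single agent in Arm 1 at the RP2D as determined in Part A (Part B, Arm 1".

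The numeric cohort-level controls belong to Part A:
- Section 3.3: "The definition of DLT applies to both the single agent and combination dose escalation arms (Part A of the study".
- Sections 3.4 and 5.6: two DLTs in up to six patients stop escalation, and "At least six patients will be treated at a dose below the MAD to define the MTD".
- Sections 5.4.2 and 5.5: staggered entry within escalation cohorts.
- Section 5.3, headed "Communication Plan where dose escalation (Part A) is to occur": dose decision meetings, timed to Week 5 of the last patient in each cohort. A halt to recruitment is among the actions they may take (5.3.2).

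The following also reach Part B:
- SAE reports within 24 hours, whatever the causality (9.7), and sponsor assessment of events with expedited SUSARs (9.3.3).
- Regular safety review, no interval stated (9.8), and interim listings at unspecified intervals (14.6).
- Optional urgent safety measures (9.9).
- A recruitment stop if the drug is judged too toxic, and a possible temporary halt (12).
- Sponsor review of the Part A arm before its Part B arm opens (3.6).
- Rules for individual patients on reduction, delay and discontinuation (5.9.5, 5.9.6).

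**The concern.** Part A ends with few patients at the chosen dose, so Part B is where an over-toxic RP2D would become visible. The plan has precise rules for the cohorts of up to six. It has none for the larger cohorts of up to 25 that follow, although safety is their primary objective. If DLT-type events cluster in a Part B arm, whether enrolment pauses, and when, depends on judgement made while the events accumulate. No threshold has been agreed beforehand and no date is set on which someone must add up the events for that arm.

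The Part B population also differs. CD32b positivity is required there but not in Part A (4.1.1), and Section 2.3 treats the relation between CD32b status and toxicity as something still to be examined.

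**Working it through.** **The plan's own figure.** The 25 per arm has no stated derivation: no target toxicity rate, unacceptable rate or precision goal is given. The only check available is 2 × 25 = 50, which matches the top of the 40 to 50 given for Part B in the synopsis. Every true rate below is therefore an assumption, shown over a range.

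**Step 1: what Part A can establish at one dose.** The input is the Section 5.6 criterion of at most one DLT in six. With true rate p and independent patients,

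P(pass) = (1 − p)^6 + 6p(1 − p)^5

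- p = 0.30: 0.118 + 0.303 = 0.42
- p = 1/3: 0.088 + 0.263 = 0.35
- p = 0.40: 0.047 + 0.187 = 0.23
- p = 0.50: 0.016 + 0.094 = 0.11

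For scale, the exact 95% interval for 1/6 runs from 0.4% to 64.1%, and for 0/6 the upper limit is 45.9%. These are pass probabilities for one dose level. They are not the chance that the dose becomes the RP2D, which also weighs PK/PD, the other arm and other trials (3.4, 5.6).

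**Step 2: what a simple count would add.** The illustration looks after 6, 12 and 18 of 25 patients and pauses at 3 or more of 6, 5 or more of 12, or 7 or more of 18. The exact binomial recursion carries forward only the paths that have not yet fired, and P(fire) is the sum of the first-fire probabilities over the three looks.

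| True rate | Look 1 | Look 2 | Look 3 | P(fire) |
|---|---|---|---|---|
| 0.10 | 0.016 | 0.002 | 0.000 | 0.02 |
| 1/6 | 0.062 | 0.016 | 0.006 | 0.08 |
| 0.20 | 0.099 | 0.031 | 0.014 | 0.14 |
| 0.25 | 0.169 | 0.065 | 0.034 | 0.27 |
| 0.30 | 0.256 | 0.106 | 0.060 | 0.42 |
| 1/3 | 0.320 | 0.133 | 0.077 | 0.53 |
| 0.40 | 0.456 | 0.177 | 0.096 | 0.73 |
| 0.50 | 0.656 | 0.188 | 0.076 | 0.92 |

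At 0.30 the rule stays silent in 1 − 0.42 = 58% of arms, so it guards mainly against clearly excessive toxicity.

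**Step 3: the trade-off.** Counts closer to Part A's two of six (2/6, 4/12, 6/18) fire with probability 0.71 at 0.30 and 0.79 at 1/3. They also fire with probability 0.12 at 0.10, 0.30 at 1/6 and 0.40 at 0.20.

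**Step 4: conditional and joint probability.** The figures in Step 2 apply once such a dose is in Part B. Multiplying the pass probability by the fire probability gives 0.42 × 0.42 = 0.18 at 0.30, 0.35 × 0.53 = 0.19 at 1/3, 0.23 × 0.73 = 0.17 at 0.40 and 0.11 × 0.92 = 0.10 at 0.50. The product treats passing one level as reaching Part B, which is a simplification.

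**The case against.** The strongest reply is that the trial is open label and the sponsor sees serious events within 24 hours, so three looks add a number and not earlier awareness. Part B is descriptive, nothing in the documents requires a formal rule, and the sponsor can halt at any time. A count fixed before Part A rates are known may also be poorly chosen. Much of this stands: it makes the gap narrow and the remedy modest. It does not supply the missing element, an agreed point at which the events in one arm are added up and acted on.

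Stronger readings are tempting and should be resisted:
- *That Part B is unmonitored or cannot be stopped.* Sections 9.3.3, 9.7, 9.8, 9.9, 12 and 14.6 contradict this.
- *That 25 patients would be exposed to an over-toxic dose, or that a trigger would save a calculable number of them.* Twenty-five is an upper bound that assumes nobody uses the discretionary stops. The proposed trigger calls a meeting and does not end the arm, so any saving is unknown.
- *That the RP2D could rest on three patients at 800 mg.* Section 5.4.3 does use the term as a design label ("If no DLTs are seen in 3 patients, further escalations will continue as 3+3 cohorts"). But Table 1 lists 3 + 3 for that cohort, and its footnote says the size "Assumes that no DLTs are encountered and is also dependant on number of patients that need to be replaced". Six is therefore the more natural reading. It also fits the stated total of 81, since 1 + 3 + 3 + 3 + 6 = 16 and 16 + 15 + 50 = 81, although the synopsis figure of 19 for that arm does not fit. The point does not depend on three.

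Sponsor SOPs and monitoring guidelines are cited (5.3.1, 14.4) but are not available here. They may set review intervals for Part B.

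**Conclusion.** The point holds at cohort level. Part B has no numeric toxicity trigger for an arm and no scheduled review of an arm; numeric rules for individual patients do exist. Oversight is continuous but discretionary. The RP2D may rest on about six patients at that dose, alongside other Part A and external data. A dose level with an assumed true DLT rate of 0.30, 1/3 or 0.40 would pass at most one of six with probability 0.42, 0.35 or 0.23.

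The benefit of a trigger is real but limited. The example counts fire with probability 0.42 at 0.30, 0.73 at 0.40 and 0.92 at 0.50, conditional on such a dose reaching Part B. The results assume independent patients and true rates that the plan does not give. The change should be made as a cheap improvement bearing on patient safety. Confidence is medium, because sponsor documents not seen may already cover part of it.

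**What to change.** In Sections 5.7 and 5.8:
1. Apply the Section 3.3 event criteria to Part B for monitoring (5.9.5 already uses the term DLT without limiting it to Part A). State explicitly that treatment-related fatal events count. In the text as extracted, fatal outcome appears under the exclusions in 3.3, which may be only a layout effect, but the wording should leave no doubt.
2. Have the existing dose decision group (5.3.1) tally, per arm, the patients with such an event by Week 5, after 6, 12 and 18 treated patients.
3. Pause enrolment to that arm for a dose decision meeting at a pre-set count with stated operating characteristics, for example 3/6, 5/12 or 7/18. The sponsor may prefer stricter counts.
4. State whether accrual is held while each group of six completes Week 5.
5. Cross-refer to the trigger from Section 12. Make clear that it calls a meeting, does not terminate the arm, and replaces neither clinical judgement, expedited reporting nor Section 9.9.

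If the monitoring guidelines already set a Part B review interval, cite it and add the count.

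The cost is protocol wording and up to three extra reviews per arm by a group that already exists. Holding accrual would slow Part B; not holding it lets some patients enter before a pause. With the example counts, the chance of an unneeded pause is 8% to 14% per arm at true rates of 1/6 to 0.20. For at least one of two independent arms it is 1 − (1 − 0.084)² = 16% at 1/6 and 1 − (1 − 0.144)² = 27% at 0.20.

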5.8 BI-1206 and rituximab combination expansion cohort (Part B, Arm 2)

On determining the RP2D of BI-1206 in combination with rituximab in Part A, Arm 2, up to 25 further patients will be enrolled into an expanded combination cohort (Part B, Arm 2) at that dose level for further evaluation of toxicity and efficacy. This cohort will include a minimum of 12 CLL and six MCL patients.

5.9 Dose modifications

Protocol defined dose modification criteria for treatment in Part B will be reviewed and updated if required based on the emerging clinical data from Part A of the trial.

For the combination arms in Parts 1 and 2, BI-1206 and rituximab should be administered independently of any dose delay to the other agent. The decision to continue with either agent alone, if the other has to be withdrawn, should be at the discretion of the investigator depending on whether there is clinical advantage to continuing with treatment.

5.9.1 Risk assessment for and management of tumour lysis syndrome

Prior to each infusion (BI-1206 or rituximab), patients should be risk assessed for tumour lysis syndrome (TLS) and treated with adequate hydration and administration of uricosurics starting 48 hours prior to the start of the infusion as well as prednisolone if appropriate. This may require a delay in the patient receiving treatment.

5.9.2 Management of infusion related reactions

Pre-medications as specified of oral paracetamol 1 gram and IV chlorphenamine 10 mg will be administered as standard at least 30 minutes prior to each BI-1206 or rituximab infusion. Hydrocortisone 100 mg IV or dexamethasone 8 mg IV may also be administered prior to administration of BI-1206 or rituximab infusion, at the same time as the chlorphenamine and paracetamol at the Investigator's discretion. Alternative premedication steroids, antihistamine and analgesics (painkillers) may be used if clinically indicated according to Investigator's judgement, after discussion and approval from the CI and Sponsor.

Patients should be carefully monitored for signs of CRS or acute infusion reaction during each infusion, e.g. signs such as urticaria, wheeze, hypotension, tachycardia, dyspnoea (shortness of breath), etc. This monitoring period will last up to at least 4 hours after the first BI-1206 infusion and at least 30 minutes after every subsequent BI-1206 infusion. For rituximab infusions, this monitoring period will last up to at least 30 minutes after the end of each infusion.

Should patients develop any of the symptoms described above despite pre-medication (with or without steroids), the infusion must be stopped immediately and IV hydrocortisone 100 mg or IV dexamethasone 8 mg administered. Alternative steroid treatment may be used if clinically indicated according to Investigator's judgement. Once the reaction has stopped, infusion of BI-1206 or rituximab may restart with a 50% reduction in the rate of infusion. If IV hydrocortisone/dexamethasone is

insufficient, the reaction may be further managed with antipyretics, anti-histamines, intra-venous sodium chloride (NaCl), bronchodilators and additional glucocorticoids as required and as per local protocols.

Patients who are to receive rituximab (Arm 2 in Parts A and B): For those patients whose lymphocyte counts are $>25 \times 10^9/L$ it is recommended to administer prednisone/prednisolone 100 mg IV shortly before rituximab infusion to decrease the rate and severity of acute infusion reactions and/or CRS. A reduced infusion rate should be considered for these patients for the first infusion and a split dosing over two days during the first week, i.e. rituximab 100mg IV Day 1 (Week 1 only) followed by rituximab 375mg/m² minus 100mg IV Day 2 (Week 1 only). The rate of infusion and confirmation of split dosing in subsequent weeks must be agreed with the Sponsor and CI prior to commencement of treatment.

Patients who are to receive BI-1206 (All patients): If IRRs are seen following Week 1 infusion, the Investigator may consider split dosing over 2 days for subsequent infusions (from Week 2 onwards) to decrease severity of reactions in subsequent doses. The rate of infusion and confirmation of split dosing must be agreed with the Sponsor and CI prior to commencement of treatment.

Patients with severe, life threatening reactions to BI-1206 or rituximab must not receive further infusions and should be withdrawn from the trial.

Investigators have the option to split the dose of BI-1206 at any point from (and including) Week 1 onwards based on clinical presentation of the patient at study entry and the Investigator's clinical judgement of what is likely to be most appropriate for an individual patient and collective study experience with giving BI-1206 to date. Once the decision to split a dose is taken, the patient must continue to receive split dosing for the duration of their study participation.

For rituximab, as per normal clinical practice, Investigators have the option to revert back to single dosing after splitting the dose.

